- 2. Participants who have an overall compliance of <80% or >120% between visits.
- 3. Participants who have taken >5 mg meeting the definition of overdose (see Section 6.8).
- 4. When participants take the Week 16 dose prior to the visit it will be considered a medication error (wrong drug administered).

Any deviation from protocol specified dosing should be recorded as a protocol deviation and the investigator or designee is to counsel the participant, legally acceptable representative/legal guardian (if applicable) and ensure steps are taken to improve compliance. In addition, if the compliance deviation reaches the thresholds defined above it should also be recorded as a medication error (see Section 8.4.10).

Note: temporary interruption to dosing per investigator judgement, as described in Section 10.10, will not be considered a protocol deviation or medication error.

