6.9.3. Prohibited During the Study

In the event of an emergency, any needed medications may be prescribed without prior approval, but the study medical monitor must be notified of the use of any prohibited medications immediately.

Prohibited Medications Not Requiring Interruption or Discontinuation of Study Treatment

- The following therapies are prohibited during the study until completion of study treatment. Participants receiving any of the following must discontinue such use immediately without interruption or discontinuation of study treatment:
- Low-to-moderate potency TCS (Class VII-IV), calcineurin inhibitors (eg, tacrolimus and pimecrolimus), or crisaborole or high potency TCS (Class III-I) administered for <7 consecutive days. TCS classes (VII-IV) are based on WHO classification of topical corticosteroids^{34,35}). See CRF guidelines.
- Topical antihistamines, tars, topical anesthetics, or antibiotic creams

- Sedating, systemic antihistamines (eg, diphenhydramine, hydroxyzine, promethazine) (nonsedating systemic antihistamines are allowed)
- Initiation of any new (ie, during the screening and treatment period) emollients/moisturizers containing additives such as ceramide, hyaluronic acid, urea, antipruritic or antiseptic agents during the screening and treatment period (patients may continue using stable doses of such emollients/moisturizers if initiated before the screening visit)

Prohibited Medications Requiring Permanent Discontinuation of Study Treatment

Use of the following therapies during the study until completion of study treatment will require permanent discontinuation of study treatment and withdrawal from the study except when specified otherwise below:

- High- to ultra-high potency TCS (Class III-I) administered for ≥7 consecutive days. TCS Classes III-I are based on WHO classification of topical corticosteroids^{34,35}. See CRF guidelines.
- Systemic corticosteroids (intranasal sprays, corticosteroid inhalers, ophthalmic and ear drop corticosteroids are allowed) (requires permanent discontinuation of study treatment but participants are not required to withdraw from the study).
- S1P receptor modulators (eg, fingolimod, ozanimod).
- α4β1 integrin receptor antagonist (eg. natalizumab).
- Anti-CD20 antibodies (eg, rituximab, ocrelizumab), anti-CD52 antibodies (eg, alemtuzumab), other cell depleting therapies (eg, bone marrow transplantation, total body irradiation).

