- Systemic immunosuppressive/immunomodulating drugs (eg, cyclosporine, azathioprine, methotrexate), including topical or oral JAK inhibitors (requires permanent discontinuation of study treatment but participants are not required to withdraw from the study).
- Any biologic treatment, anti-IL4/13 antibodies (eg, dupilumab), anti-IL13 antibodies (eg, tralokinumab, lebrikizumab), anti-IL17A antibodies (eg, secukinumab), anti-IL12/23 antibodies (eg, ustekinumab), anti-IL31 antibodies (eg, nemolizumab), anti-IL23 antibodies (eg, risankizumab) requires permanent discontinuation of study treatment, but participants are not required to withdraw from the study.
- Any IV medications taken in response to serious infection that required hospitalization or treatment.

- Moderate/strong inhibitors or inducers that inhibit or induce at least 2 of the following: cytochrome P450 (CYP)2C8, CYP2C9, and CYP3A4 (e.g., fluconazole, rifampin, enzalutamide, Section 10.8.1).
- Live-attenuated replication-competent vaccines starting 6 weeks prior to baseline (Day 1), during study treatment and for 4 weeks after the last dose of study treatment.
- Start, stop, or change in dosage of any anti-arrhythmic drugs (Class I to IV) within 1 week before or after treatment initiation or reinitiation following dose interruption of a duration requiring in-clinic cardiac monitoring (Section 6.1.1).
- Any investigational drug other than the study treatment.

Participants who complete the treatment period no longer need to abstain from the medications that were prohibited during the treatment periods, unless noted otherwise (eg, live attenuated vaccines for 4 weeks after the last dose of study treatment).

For prohibited concomitant procedures:

- Participants may not undergo phototherapy for AD or artificial tanning (beds, booths, or lamps), including psoralen and ultraviolet A, ultraviolet B, tanning booth, and excimer laser.
- Participants should not take bleach baths.
- Participants should not undergo cell depleting therapies (eg, bone marrow transplantation, total body irradiation).
- Participants should not undergo major elective surgery while on study treatment.
- Participants may not donate blood during the study and for 30 days after the last dose of study treatment.
- Participants may not donate sperm, or oocytes during the study and for 28 days after the last dose of study treatment.

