7. DISCONTINUATION OF STUDY INTERVENTION AND PARTICIPANT DISCONTINUATION/WITHDRAWAL

7.1. Discontinuation of Study Intervention

It may be necessary for a participant to permanently discontinue study intervention. Reasons for permanent discontinuation of study intervention include the following:

- Adverse events noted below (participants with AEs listed below, irrespective of
 causality, will be discontinued from the study intervention) NOTE: Sub bullets below
 are examples and are not intended to be an all-inclusive list.
 - Second episode of confirmed Grade 4 lymphopenia in the same participant (Protocol Sections 10.10.1, 10.10.2)
 - Repeated episode of a serious infection for the same participant (Protocol Section 10.10.2)
 - o Diagnosis of PML (Protocol Section 10.11)
 - Diagnosis of PRES (Protocol Section 8.4.8)
 - ECG changes (Protocol Section 7.1.3)
 - Suspected intolerance associated with first dose cardiac effects (Protocol Section 10.10.3.2)
 - o Malignancy (Protocol Section 8.4.8)
 - o HBV DNA above LLQ (Protocol Section 8.3.7)
 - O Active, latent, or inadequately treated TB infection (Protocol Section 8.3.5)

 PFIZER CONFIDENTIAL

 CT02 GSOP Clinical Protocol Template Phase 1.2.3.4 (01.4 pril 2022)

- o Clinically significant respiratory AE and or a decline in confirmed PFT values (FEV1 and/or FVC below 50% of the predicted values; Protocol Section 10.10.4)
- o Confirmed macular edema (Protocol Section 10.10.5)
- Drug-induced liver injury confirmed cases after all results of reasonable investigations have been received as per Protocol Section 10.5, and alternative etiology have been excluded (Protocol Section 10.10.5)
- Clinically significant safety concern as per investigator's judgement at Week 16 (Protocol Section 7.1.1)
- Death
- Lost to follow up
- Physician decision
- Pregnancy
- Protocol deviation
- Study terminated by Sponsor
- Withdrawal by participant
- Lack of Efficacy

Discontinuation of study intervention does not represent withdrawal from the study. If study intervention is permanently discontinued, the participant should remain in the study to be evaluated for safety. See the SoA for data to be collected at the time of discontinuation of study intervention and follow-up for any further evaluations that need to be completed.

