10.10.2. Serious Infections Monitoring

Low lymphocyte counts observed with the use of other S1P receptor modulators in patients with multiple sclerosis have been associated with serious and atypical infections. ^{4,5,46} Investigators should remain vigilant in monitoring for signs and symptoms of serious and atypical infections during the study and after discontinuation of study treatment. Serious infection monitoring (refer to definition for Serious Adverse Events in Section 10.3.2) requires a temporary interruption of study intervention. Study intervention cannot be restarted until the serious infection has resolved per investigator judgement (investigator may discuss restarting study intervention with the medical monitor, if needed). If the participant cannot be restarted on study intervention, then the participant must be permanently discontinued.

Participants will be queried for signs and symptoms of PML. If a participant exhibits signs and symptoms suspicious for PML, study treatment must be interrupted and cannot be restarted until diagnostic evaluation is completed and PML has been excluded. The study medical monitor should be informed of any suspected cases of PML. Refer to Section 10.11 for signs and symptoms of PML and a PML case evaluation algorithm. In the evaluation and management of treatment emergent infections, the Investigator may consult with infectious disease or relevant experts, as needed.

All radiologic images (eg, magnetic resonance imaging, computer tomography, X rays) and diagnostic laboratory test results performed by local laboratories/facilities should be retained as source documents by study sites and made available upon request by the Sponsor for central adjudication as needed. All infections that develop during the study will be reported as AEs on the AE eCRF page.

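### After a first serious infection treated intravenously, Protocol 6.9.3 orders a permanent stop and study withdrawal, 10.10.2 allows restart and 7.1 keeps the participant in follow-up; no text ranks them

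*Protocol*

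**What the plan says.** Protocol 6.9.3 has a list of therapies whose use "will require permanent discontinuation of study treatment and withdrawal from the study except when specified otherwise below". One bullet on it is "Any IV medications taken in response to serious infection that required hospitalization or treatment". The systemic corticosteroid, systemic immunosuppressant and biologic bullets each add that the participant need not leave the study. The IV bullet adds nothing, and does not separate a first episode from a later one.

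Protocol 10.10.2 uses the SAE definition to identify serious infections, and says that such an infection "requires a temporary interruption of study intervention. Study intervention cannot be restarted until the serious infection has resolved per investigator judgement". It then says: "If the participant cannot be restarted on study intervention, then the participant must be permanently discontinued". IV treatment is not mentioned.

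Protocol 7.1 refers to 10.10.2 and gives as its infection example "Repeated episode of a serious infection for the same participant", in a list that it calls not all-inclusive. It also says: "If study intervention is permanently discontinued, the participant should remain in the study to be evaluated for safety".

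Three other places bear on the point:

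- Section 6.9.3 says that "the study medical monitor must be notified of the use of any prohibited medications immediately".
- Section 10.8.1, in the drug-interaction appendix, has the investigator judge ongoing participation after any prohibited medication, once the sponsor has been consulted.
- SAP Appendix 4 counts prohibited medication as an intercurrent event only when clinical review has verified a protocol deviation in a dedicated subcategory.

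**The concern.** A participant with a first serious infection who receives IV treatment is covered by rules that do not agree. Under 6.9.3, study drug ends for good and the participant leaves the study. Under 10.10.2, drug is interrupted and may be restarted. Under 7.1, a participant who stops drug stays in for safety evaluation.

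Infections are an adverse event of special interest for etrasimod (Protocol 8.4.8), and lymphocyte lowering is its expected pharmacological effect (2.3.1). Whether to give the drug again after such an event should have one written answer. As it stands, a site that restarts breaches 6.9.3, and a site that withdraws the participant departs from 7.1.

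**Working it through.** The point is textual apart from its size, so the rules are set side by side first.

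**1. Do the triggers overlap?** Section 10.10.2 covers serious infections as defined in 10.3.2, which includes inpatient hospitalization. The 6.9.3 bullet covers IV treatment of a serious infection that needed hospitalization or treatment. A first serious infection treated intravenously meets both.

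**2. What does each section require?**

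| Section | Study drug | Study participation |
|---|---|---|
| 6.9.3, IV bullet | Permanent stop | Withdraw; no exception stated |
| 10.10.2 | Interrupt; restart possible after resolution; permanent stop if restart is not possible | Not addressed |
| 7.1 | Permanent stop on a repeated episode (example only) | Remain for safety evaluation after a stop |
| 10.8.1 | Not addressed directly | Investigator's judgement after consulting the sponsor |

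**3. Is the missing exception deliberate?** The permanent-discontinuation list in 6.9.3 has 12 bullets. Three carry the withdrawal exception, and 12 − 3 = 9 do not, including the IV bullet. The exception clause in the lead-in most naturally refers to the bullets that follow it, so it does not bring in 10.10.2 or 7.1.

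**4. Does any text rank the sections?** Neither 6.9.3 nor 10.10.2 refers to the other. Notifying the medical monitor (6.9.3), and contacting the monitor about medical interruptions of 7 days or more (7.1.7), bring in a second opinion but do not say which rule that person should apply.

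**5. What follows for data and analysis?**

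- *Safety follow-up.* AE collection runs for at least 4 weeks after the last dose and ends sooner only if consent is withdrawn (8.4.1). After a stop, only the early termination visit and the 2- and 4-week follow-up visits remain (1.3.2 and 1.3.3). The withdrawal wording therefore puts little follow-up at risk.
- *Estimand E1.* A permanent stop before Week 16 makes the participant a non-responder (9.1.1.1). A participant who restarts is a non-responder through the prohibited-medication event only if clinical review confirms it (SAP Appendix 4). With 30 per arm, one participant is 1/30 = 3.3 percentage points of an arm's response rate.

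**6. How many participants?** The documents give no rate of serious infection, and Protocol 2.3.1 reports no clinically relevant infection signal in the Phase 2 AD study. Assume that a proportion r of participants, between 0.5% and 2%, has a first serious infection treated intravenously. Expected count = n × r; chance of at least one in Part 1 = 1 − (1 − r)^60.

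| r | Part 1 (n = 60) | Chance of at least one in Part 1 | Part 2 (n = 340, if opened) | Total (n = 400) |
|---|---|---|---|---|
| 0.5% | 0.3 | 0.26 | 1.7 | 2 |
| 1% | 0.6 | 0.45 | 3.4 | 4 |
| 2% | 1.2 | 0.70 | 6.8 | 8 |

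**The case against.** The best defence is that 6.9.3 is the specific rule and 10.10.2 the general one. Section 10.10.2 makes resolution a necessary condition for restart and gives no right to it. A participant who received a listed therapy could be one who cannot be restarted. The examples in 7.1 are not exhaustive. Table 1 in 6.9.2 uses nearly the same IV wording as a 4-week washout, which fits a deliberate stricter tier for IV-treated infection. Section 10.8.1, read with the duty to notify the monitor, gives sites a route to a decision.

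Much of this stands. The drug actions can be reconciled that way, but the protocol nowhere says that they should be. Restart and the repeated-episode rule would then apply only to serious infections managed without IV drugs. The Table 1 wording is equally consistent with a bullet carried over from the washout list. Section 10.8.1 adds a third, discretionary rule, at odds with the mandatory wording of 6.9.3. Even on the stricter-tier reading, the order to withdraw still contradicts 7.1.

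A reader might also infer that restart is already authorised, because Section 6.5 says that "temporary interruption to dosing per investigator judgement, as described in Section 10.10, will not be considered a protocol deviation or medication error". That note concerns missed doses. It does not address restarting after a prohibited IV drug, so it does not settle the matter.

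**Conclusion.** The inconsistency is real and should be corrected. For the same participant, the protocol gives different instructions on study drug and contradictory ones on staying in the study. Few participants are likely to be affected, and the effect is mainly on study-drug handling. The counts above rest on an assumed rate with no source in the documents and no time basis, so they give an order of magnitude only.

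Three stronger readings are not supported:

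- *Sites have no route to a decision.* They have one through the monitor, the sponsor and 10.8.1; what is missing is the rule to apply.
- *Safety follow-up would be largely lost.* The AE collection period does not depend on this wording, and few visits remain after a stop.
- *E1 comes out the same whether drug is stopped or restarted.* Protocol 9.1.1.1 suggests this, because any prohibited medication before Week 16 means non-response. Under SAP Appendix 4, however, a restarted participant's status depends on clinical review.

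The documents also do not show whether the sponsor intends restart or a permanent stop after IV treatment.

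**What to change.** In the 6.9.3 IV bullet, state that withdrawal from the study is not required, as the corticosteroid, immunosuppressant and biologic bullets already do.

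Then give one drug action in 6.9.3, 10.10.2 and 7.1. The sponsor should choose between:

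- interruption managed under 10.10.2, with a permanent stop on a repeated episode or if restart is not possible; or
- a permanent stop after IV treatment, stated in 10.10.2 and 7.1 as well as 6.9.3.

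Finally, state whether IV treatment of a serious infection counts as the prohibited-medication intercurrent event; SAP Appendix 4 is the natural place.

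The cost is one amended bullet in 6.9.3, one sentence each in 10.10.2 and 7.1 if a permanent stop is intended, and one sentence on the intercurrent event. No procedure, visit or analysis is added.

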6.9.4. Rescue Medicine

Medicated and non-medicated rescue medications are not permitted during the Part 1 DB portion. For Part 1 OLE and Part 2 medicated and non-medicated topical treatments for AD will be permitted at the discretion of the investigator and in accordance with their usual practice.

6.9.5. Permitted During the Study

Vaccinations are permitted as clinically indicated except for live-attenuated replication-competent vaccines. At this time, there are no data on the effect of etrasimod treatment on vaccine efficacy and safety including severe acute respiratory system

coronavirus 2 (SARs-CoV-2) vaccines to protect against COVID-19. It is recommended that participants receive a vaccination against COVID-19 to decrease the risk of contracting SARs-CoV-2.

The American Academy of Dermatology has published recommendations that advise patients on immunomodulating drugs to be vaccinated as "The CDC does not consider COVID-19 vaccine to be contraindicated in persons taking biologic or traditional immunosuppressive medications, hedgehog pathway inhibitors, and PD-1 inhibitors".

If a participant receives a vaccination, the vaccination date and type (eg, SARS-CoV-2) should be captured in the Concomitant Medication log/eCRF. The vaccine brand, manufacturer, and lot number (if available) should be captured in the source documentation.

Hormonal contraceptives that meet the requirements of this study are allowed to be used in participants who are WOCBP (see Appendix 4) and should be captured on the Concomitant Medication log/eCRF.

7. DISCONTINUATION OF STUDY INTERVENTION AND PARTICIPANT DISCONTINUATION/WITHDRAWAL

7.1. Discontinuation of Study Intervention

It may be necessary for a participant to permanently discontinue study intervention. Reasons for permanent discontinuation of study intervention include the following:

- Adverse events noted below (participants with AEs listed below, irrespective of
 causality, will be discontinued from the study intervention) NOTE: Sub bullets below
 are examples and are not intended to be an all-inclusive list.
 - Second episode of confirmed Grade 4 lymphopenia in the same participant (Protocol Sections 10.10.1, 10.10.2)
 - Repeated episode of a serious infection for the same participant (Protocol Section 10.10.2)
 - o Diagnosis of PML (Protocol Section 10.11)
 - Diagnosis of PRES (Protocol Section 8.4.8)
 - ECG changes (Protocol Section 7.1.3)
 - Suspected intolerance associated with first dose cardiac effects (Protocol Section 10.10.3.2)
 - o Malignancy (Protocol Section 8.4.8)
 - o HBV DNA above LLQ (Protocol Section 8.3.7)
 - O Active, latent, or inadequately treated TB infection (Protocol Section 8.3.5)

 PFIZER CONFIDENTIAL

 CT02 GSOP Clinical Protocol Template Phase 1.2.3.4 (01.4 pril 2022)

- o Clinically significant respiratory AE and or a decline in confirmed PFT values (FEV1 and/or FVC below 50% of the predicted values; Protocol Section 10.10.4)
- o Confirmed macular edema (Protocol Section 10.10.5)
- Drug-induced liver injury confirmed cases after all results of reasonable investigations have been received as per Protocol Section 10.5, and alternative etiology have been excluded (Protocol Section 10.10.5)
- Clinically significant safety concern as per investigator's judgement at Week 16 (Protocol Section 7.1.1)
- Death
- Lost to follow up
- Physician decision
- Pregnancy
- Protocol deviation
- Study terminated by Sponsor
- Withdrawal by participant
- Lack of Efficacy

Discontinuation of study intervention does not represent withdrawal from the study. If study intervention is permanently discontinued, the participant should remain in the study to be evaluated for safety. See the SoA for data to be collected at the time of discontinuation of study intervention and follow-up for any further evaluations that need to be completed.

In the event of discontinuation of study intervention, it must be documented on the appropriate CRF/in the medical records whether the participant is discontinuing further receipt of study intervention or also from study procedures, further study follow-up, and/or future collection of additional information.

7.1.1. Discontinuation after Part 1 DB (Week 16) due to a Clinically Significant Safety Concern

Per investigator's judgement, participants must permanently discontinue study intervention at the Part 1 Week 16 visit if they experienced an AE and/or SAE during the DB study portion that was a clinically significant safety concern for study continuation which may or may not have resulted in study treatment interruption. The investigator may seek medical monitor's consideration, if needed, to determine participant continuation.

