10.10.4. Pulmonary Function Monitoring

Based on changes in pulmonary function observed with the use of S1P receptor modulators for relapsing multiple sclerosis^{4,5}, pulmonary function will be assessed in this study.

Participants experiencing clinically significant dyspnea or other respiratory AEs, may need to have additional PFT testing as clinically indicated. Severity of respiratory AEs should be categorized using the CTCAE scale. Investigators should consider interruption of study treatment when there is a clinically significant respiratory AE that leads to limitations in self-care activities of daily living and is associated with PFT decrease. Participants experiencing a confirmed decline in PFT values (FEV1 and/or FVC) below 50% of the predicted values must be discontinued from study treatment and scheduled for a follow-up visit. The decision to interrupt study treatment should be discussed with the blinded Pfizer medical monitor. Participants should be promptly referred to a pulmonologist for further evaluation and treatment. The pulmonologist should be provided with a standard referral letter explaining the reason for the referral along with information about the investigational drug. Clinically significant respiratory AEs should be followed until there is stability, improvement, or resolution.

Reinitiation of study treatment can only be considered if the respiratory AE has improved, stabilized, and/or resolved; the individual risk benefit is favorable (as determined by the Investigator, in agreement with the pulmonologist); and after discussion with the blinded Pfizer medical monitor. The investigator is to ensure first dose cardiac monitoring (Section 10.10.3) is implemented upon drug reinitiation if consecutive days of study treatment are missed as described in Section 7.1.7.

Information regarding the collection of PFTs is provided in Section 8.3.9. PFTs will be performed at timepoints specified in the SoA.

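### Protocol Section 7.1 makes a clinically significant respiratory AE a permanent stop on its own, while Section 10.10.4, which it cites, calls only for considering interruption, with restart allowed

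*Protocol*

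**What the plan says.** Protocol Section 7.1 gives the reasons for permanent discontinuation of study intervention. Participants with a listed AE, whatever its cause, "will be discontinued from the study intervention". A note adds that the sub-bullets "are examples and are not intended to be an all-inclusive list". One sub-bullet reads "Clinically significant respiratory AE and or a decline in confirmed PFT values", gives the threshold in brackets (FEV1 and/or FVC under 50% of predicted) and cites Section 10.10.4.

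Section 10.10.4 contains two separate rules.

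- **Respiratory AE.** "Investigators should consider interruption of study treatment when there is a clinically significant respiratory AE", and only where the event leads to "limitations in self-care activities of daily living and is associated with PFT decrease". There is a way back: "Reinitiation of study treatment can only be considered if the respiratory AE has improved, stabilized, and/or resolved". Restart also needs a favourable individual risk-benefit judgement by the investigator, agreed with the pulmonologist, and discussion with the medical monitor.
- **Lung function.** Participants with a confirmed fall in FEV1 and/or FVC "below 50% of the predicted values must be discontinued from study treatment". No AE is needed.

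The AESI list in protocol Section 8.4.8 marks macular edema, PML, PRES and malignancies with an asterisk, meaning that the diagnosis requires a permanent stop. Pulmonary events have no asterisk and point to Section 10.10.4. SAP Section 3.5.2 uses the same marking. The asterisk footnote in Section 8.4.8 also sends the reader to Section 7.1 for further AEs that require discontinuation.

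**The concern.** A site faced with a clinically significant respiratory AE and FEV1 and FVC still above 50% of predicted finds two instructions. Section 7.1 tells it to stop treatment for good. Section 10.10.4 tells it, at most, to consider a pause and then a restart. One site may do the first and another the second for the same event.

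Two things depend on the choice. The first is whether that participant continues on treatment. The second is a reported outcome: AEs leading to discontinuation of study treatment are part of a primary safety endpoint for Part 1 OLE and Part 2 (protocol Section 3). Pulmonary events are also an AESI for this drug, and the risk table in protocol Section 2.3.1 relies on clearly defined stopping criteria as a mitigation.

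**Working it through.** The plan gives no figure to reproduce here, so the check is a comparison of the two rules, case by case. Let A be a clinically significant respiratory AE, and P a confirmed FEV1 and/or FVC below 50% of predicted.

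| Case | 7.1 read as and/or | 7.1 read as and | 10.10.4 |
|---|---|---|---|
| A without P; self-care limited and some PFT decrease | Permanent stop | Not triggered | Consider interruption; restart possible |
| A without P; self-care not limited or no PFT decrease | Permanent stop | Not triggered | Further PFT as clinically indicated; no interruption advised |
| P without A | Permanent stop | Not triggered | Must discontinue |
| A with P | Permanent stop | Permanent stop | Must discontinue |

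**Read as and/or.** The sections agree wherever P is present; the 50% threshold is identical. They conflict in both rows with A alone. There, Section 7.1 is mandatory and permanent, while Section 10.10.4 is discretionary and reversible in the first row and advises no interruption in the second.

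**Read as and.** The bullet omits the stop for P alone. Nothing conflicts, though. Section 7.1 says its sub-bullets are not exhaustive, and Section 10.10.4 requires the stop in its own right. On this reading the bullet is an incomplete example.

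**Comparison with neighbouring bullets.** The other bullets fit the sections they cite. Confirmed macular edema is a permanent stop in both Section 7.1 and Section 10.10.5. The lymphopenia bullet is limited to a second confirmed Grade 4 episode, as in Section 10.10.1. The serious-infection bullet is limited to a repeated episode, which leaves room for the interrupt-and-restart rule in Section 10.10.2. The ECG bullet states no criterion and leaves it to Section 7.1.3. The respiratory bullet instead states an AE trigger of its own, with no qualification.

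**Scale.** The documents give no respiratory AE rate, so the number affected cannot be estimated. One participant recorded as a discontinuation instead of an interruption moves the percentage discontinuing due to an AE by:

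- 1/30 = 3.3 percentage points in a Part 1 group of about 30;
- 1/340 = 0.3 percentage points in Part 2, with about 340 participants, if Part 2 goes ahead.

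Any single reclassified participant would produce the same change. These figures give the scale and are not evidence that the bullet will have an effect.

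**The case against.** The strongest reply is that Section 7.1 is shorthand and Section 10.10.4 is plainly the working rule. The ECG bullet, taken literally, would permanently stop anyone with an ECG change. Yet Section 7.1.3 requires interruption for a confirmed QTc above 500 ms, allows restart, and makes the stop permanent only on recurrence. The bullets therefore have to be read with their cross-references. The AESI marking in Section 8.4.8 and SAP Section 3.5.2 leaves pulmonary events out of the stop-on-diagnosis group, and the Schedule of Activities and Section 8.3.9 send sites to Section 10.10.4 for respiratory symptoms.

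Much of this stands: it makes Section 10.10.4 the likely intent. It does not remove the conflict. Unlike the ECG bullet, the respiratory bullet states its own trigger. The Section 8.4.8 footnote sends readers to Section 7.1 for further AEs requiring discontinuation, and Section 2.3 describes the stopping criteria as those in Section 7. No text says which section governs.

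The second reply is that existing controls limit divergence: "The decision to interrupt study treatment should be discussed with the blinded Pfizer medical monitor". Sections 7.1.7 and 10.10 also require contact with the study medical monitor for medical interruptions of 7 days or more, and Section 10.10 names that monitor for all other safety concerns. This reduces the problem. It does not remove it, because a site following Section 7.1 is stopping, not interrupting, and nothing tells the monitor which rule to apply.

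A reader might infer that the bullet contradicts Section 10.10.4 on either reading of the conjunction. It does not; the second reading leaves an omission that Section 10.10.4 fills. A reader might also infer a safety gap. The conflict runs the other way, towards an extra stop, and confirmed FEV1 and/or FVC below 50% of predicted leads to discontinuation in every case.

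**Conclusion.** The conflict is real but narrow. In its natural and/or sense, the Section 7.1 bullet turns a respiratory AE alone into a mandatory permanent stop, which the section it cites does not support. The conclusion rests on the wording alone.

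The size is unknown and may be zero. What is at stake is uniform handling of the AE and the count of AEs leading to discontinuation in Part 1 OLE and Part 2.

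A reader might go further and infer a threat to the Week 16 IGA result, since stopping treatment before Week 16 makes a participant a non-responder under Estimand E1 and interruption is not a listed intercurrent event. The documents do not support that: they give no respiratory AE rate and nothing that links such AEs to response. This is a minor stopping-rule correction. It does not question the design, the estimands or the analysis.

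**What to change.** Replace the respiratory bullet in Section 7.1 with:

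> Confirmed FEV1 and/or FVC below 50% of predicted; or a clinically significant respiratory AE for which study treatment was interrupted and cannot be restarted under Section 10.10.4.

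This keeps the stop for lung function alone, leaves the AE to the interrupt-and-restart rule, and follows the form already used for serious infections in Section 10.10.2.

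If the clinical team does intend a permanent stop for the AE alone, Section 10.10.4 must say so and lose its interruption and restart text. The missing asterisk for pulmonary events in Section 8.4.8 and SAP Section 3.5.2 should then be reconsidered.

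The cost is one reworded bullet in the next planned amendment, with IRB/EC approval, and health authority approval if the amendment is substantial (Section 10.1.1). Data collection, sample size and analysis do not change.
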